5.7. Primary Outcome and Methodology

The primary objective is to compare the HbA1c change from baseline to Week 26 between LY3209590 and insulin degludec and will be based on the primary estimand described below.

The primary estimand is the treatment differences in the change in HbA1c from baseline to 26 weeks for the targeted study population if all patients would adhere to the treatment without intercurrent events. The analysis data will include data up to the discontinuation of study treatment for the Efficacy Population with baseline and at least one non-missing postbaseline measurement. There may be missing values due to the early discontinuation of study treatment. The MMRM model will be used with the HbA1c changes at Week 6, 12, 16 and 26 (the primary endpoint) and the missing values will be imputed implicitly in the MMRM analysis under the assumption of missing at random. The MMRM model will include treatment (LY3209590 Algorithm 1, insulin degludec), country, visit, and treatment by visit interaction and the baseline value of the dependent variable as the fixed effects. The HbA1c is reported in unit of % and will be converted to the unit of mmol/mol using the following formula: HbA1c in mmol/mol = 10.93*HbA1c in % - 23.5 (<http://www.ngsp.org/ifccngsp.asp>). HbA1c analysis will be conducted based on both units.

In the MMRM model, the within-patient errors are modeled as an unstructured variance-covariance matrix. If the analysis fails to converge, the following variance-covariance matrix will be used (in order) until one converges:

1. Toeplitz with heterogeneity
2. autoregressive with heterogeneity
3. compound symmetry with heterogeneous variances
4. Toeplitz
5. autoregressive
6. compound symmetry without heterogeneous variances

The Kenward-Roger approximation will be used to estimate denominator degrees of freedom for the MMRM models. The following is an example SAS code:

```
proc mixed data=DATA;
  class TREATMENT STRATIFICATIONS VISIT PATIENT;
  model HbA1c=BASELINE TREATMENT STRATIFICATIONS VISIT
    VISIT*TREATMENT / solution ddfm=kr;
  repeated VISIT / subject=PATIENT type=un;
  lsmeans TREATMENT*VISIT/ pdiff cl alpha=0.1 om=DATA;
run;
```

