5.12. Subgroup Analyses

The subgroups will be defined as:

- Body mass index (<30, ≥ 30)
- Baseline HbA1c (<8.5% and $\geq 8.5\%$)
- Region (US and non-US)

The outcome measures included in the subgroup analyses are:

[figure not shown]
- HbA1c and change in HbA1c from baseline to up to 26 weeks
- Documented hypoglycemia, non-nocturnal and nocturnal hypoglycemia rates (<54 mg/dL [3.0 mmol/L]) during 0-26 weeks.

Analyses for HbA1c and its change will be performed examining the 3-way interaction of the primary treatment arms, visit and the subgroup variable using the same MMRM model described for the primary analysis. This model will include the same fixed effects given for the primary analysis model plus factors of subgroup, 2-way interaction of subgroup and treatment, 2-way interaction of subgroup and visit, and 3-way interaction of treatment, visit and the subgroup.

The hypoglycemia rates will be analyzed using a negative binomial regression including the same fixed effects for hypoglycemia event analyses plus factors of subgroup, 2-way interaction of subgroup and treatment.

The interaction effects will be evaluated using a significance level of 0.1, unadjusted. If the interaction effect is significant ($p<0.1$), separate analysis without the terms related with the subgroup will be performed for each subpopulation.

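### About 12 subgroup interaction tests at an unadjusted 0.10 decide which separate subgroup analyses are produced; with no true interaction, the chance of at least one false trigger is about 0.45 to 0.72, and the estimates shown are selected by the result

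*SAP*

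**What the plan says.** SAP 5.12 names three two-level subgroup variables: BMI at 30, baseline HbA1c at 8.5%, and US versus non-US. The outcomes are "HbA1c and change in HbA1c from baseline to up to 26 weeks" and "Documented hypoglycemia, non-nocturnal and nocturnal hypoglycemia rates (<54 mg/dL [3.0 mmol/L]) during 0-26 weeks".

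For HbA1c, the primary MMRM is extended with subgroup terms and the section says that the three-way interaction of treatment, visit and subgroup is examined. For the hypoglycemia rates, a negative binomial model gains the subgroup and its interaction with treatment. The testing rule is "The interaction effects will be evaluated using a significance level of 0.1, unadjusted". If a test has p<0.1, "separate analysis without the terms related with the subgroup will be performed for each subpopulation".

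The section gives no count of tests, no overall error rate and no exploratory label. It has no rule for presenting subgroup estimates when the interaction is not significant.

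**The concern.** Two features combine. First, a family of tests is run with no control of the chance that at least one is positive. The SAP discloses this openly. Second, the separate within-subgroup analyses exist only if the test is positive. Disclosing the lack of adjustment does not deal with that: whether stand-alone subgroup results appear depends on how large the apparent difference was in this sample.

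At stake is how the subgroup results are read. A clinical study report produced to this rule could show a separate analysis for one or two splits and nothing comparable for the rest. A reader would have no ready way to see that the displayed split was the largest of a dozen. Hypoglycemia is a secondary safety endpoint, and SAP 5.10.3.2 treats Level 2 events (below 54 mg/dL) as clinically significant, so a spurious subgroup finding there could be taken seriously.

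**Working it through.** The SAP gives no figure of its own on this point to reproduce, so the check starts from the count.

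**Number of tests.** There are 3 subgroup variables and 4 distinct outcomes. HbA1c value and HbA1c change count once: the model in SAP 5.7 has the "baseline value of the dependent variable as the fixed effects", so both give the same interaction test, and the mmol/mol version is a linear rescaling. The other three outcomes are the documented, non-nocturnal and nocturnal rates. 3 × 4 = 12. The expected number of false positives is 12 × 0.10 = 1.2, whatever the correlation.

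The SAP does not say whether the two-way treatment-by-subgroup term for HbA1c could also trigger a separate analysis. If it could, the count would be 15.

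**Chance of at least one false trigger, no true interaction.** If the tests are independent, 1 − 0.9^12 = 0.72 (for 15 tests, 1 − 0.9^15 = 0.79).

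The tests are not independent. By SAP 5.10.3.2 nocturnal and non-nocturnal events are the two parts of documented events. The documents give no correlations, so a range was assumed and 12 correlated normal test statistics were simulated with rejection at |Z| > 1.645:

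| Documented / non-nocturnal | Documented / nocturnal | Nocturnal / non-nocturnal | HbA1c / hypoglycemia | Between subgroup variables | Chance of ≥1 trigger |
|---|---|---|---|---|---|
| 0 | 0 | 0 | 0 | 0 | 0.72 |
| 0.90 | 0.50 | 0.30 | −0.2 | 0 | 0.63 |
| 0.95 | 0.60 | 0.40 | −0.2 | 0.1 | 0.61 |
| 0.98 | 0.70 | 0.55 | −0.2 | 0.2 | 0.58 |
| 0.98 | 0.80 | 0.70 | −0.2 | 0.3 | 0.55 |
| 0.99 | 0.90 | 0.85 | −0.3 | 0.3 | 0.52 |

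The figure falls to 0.45 to 0.47 only near redundancy. Examples are a correlation of 0.8 between all outcomes and 0.5 between subgroup variables, or three hypoglycemia rates that act as one (six effective tests: 1 − 0.9^6 = 0.47). Patient-level simulations with overdispersed counts, where documented = nocturnal + non-nocturnal, gave 0.59 to 0.67. The individual count tests in those runs rejected slightly more often than 0.10, which pushes that range up.

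**Exaggeration after selection.** For the nine hypoglycemia tests the interaction has 1 degree of freedom. With no true interaction, the mean of |Z| given p<0.1 is 2φ(1.645)/0.10 = 2 × 0.103/0.10 = 2.06. Without selection it is √(2/π) = 0.80. A triggered interaction on the log-rate scale is therefore on average 2.06/0.80 = 2.6 times as large as an unselected one would be by chance.

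**The HbA1c test.** Post-baseline visits are at Weeks 6, 12, 16 and 26. The three-way interaction with a two-level subgroup has (4 − 1) × (2 − 1) = 3 degrees of freedom, and it asks whether the subgroup difference in treatment effect changes across visits. If that difference is the same at every visit, all three contrasts are zero. The test then rejects only at its 10% error rate, however large the constant difference is. For HbA1c the condition therefore admits false positives and is also blind to a steady subgroup difference.

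**The case against.** The strongest case is that little turns on this. Testing at 0.10 matches the trial-wide level, and the absence of adjustment is stated outright. No subgroup comparison is among the objectives, and the only rule for declaring success (SAP 5.7) concerns the overall comparison. The interaction model is fitted for every subgroup variable and outcome whatever the p-value, subgroup estimates can be read from it, and nothing forbids showing them. All of that stands. It limits the point to selective reporting of secondary results; it does not justify a written rule that makes the separate analyses depend on significance.

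A reader might infer more than the documents support in three ways.

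- *That a false trigger is more likely than not.* This usually holds under the assumed correlations, but not near redundancy, and it is conditional on there being no true interaction.
- *That a false HbA1c trigger needs an apparent Week 26 subgroup difference of at least about 0.53 to 0.61 percentage points.* That calculation (SD 1.1, 95 per arm, splits of 50/50 to 25/75) describes a 1-degree-of-freedom Week 26 contrast. The SAP specifies the 3-degree-of-freedom test, which has no such minimum. Simulating that test with assumed between-visit correlations of 0.5 to 0.85, 78% to 87% of false triggers had a Week 26 difference below the supposed minimum, and the mean was 0.28 to 0.39. Power figures from the 1-degree-of-freedom contrast fail for the same reason.
- *That the exaggerated difference exceeds the 0.4 non-inferiority margin.* The margin applies to one treatment difference. An interaction is a difference between two such differences, so they are not on the same footing.

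**Conclusion.** The point holds as a matter of reporting. SAP 5.12 sets about 12 interaction tests at an unadjusted 0.10 and makes separate subgroup analyses conditional on significance. With no true interaction, the chance of at least one false trigger is about 0.45 to 0.72, most plausibly 0.55 to 0.63, against 0.10 for a single test. The range rests on assumed correlations between outcomes and between subgroup variables. The count of 12 is derived from the section, not stated in it.

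The separate estimates that follow are selected by the result and exaggerated on average, not in every instance. The 2.6-fold figure applies to the hypoglycemia interactions when none is real; no Week 26 HbA1c magnitude should be attached to this point. The documents also do not show that other subgroup estimates will be withheld, only that there is no commitment to report them. The primary non-inferiority conclusion is not affected.

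**What to change.** Delete the p<0.1 condition in SAP 5.12. For all three subgroup variables and all four outcomes, report the treatment effect in each subgroup with its 90% CI from the interaction model already specified: at Week 26 for HbA1c, and over 0–26 weeks for the hypoglycemia rates. Put the interaction p-value alongside and, for HbA1c, state which interaction term it tests. Label the section exploratory and unadjusted for multiplicity, and give the number of tests.

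A stricter alpha is not needed. The cost is SAP wording, a few additional LSMEANS or ESTIMATE statements in models already planned, and a forest plot per outcome. No new data are required. The only downside is a few more displays.
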